## Abstract

**Importance.** Enhancing the management of messages from patients and providing virtual options for urgent care are top priorities for The Permanente Medical Group (TPMG) and Kaiser Foundation Hospitals/Health Plan (KFH/P).

**Objective.** To compare pharmacist management of e-visit requests for Paxlovid for COVID-19 with management by adult and family medicine physician pools regarding costs, time, clinical outcomes, and patient and clinician satisfaction.

**Design, setting, and participants.** This cluster randomized clinical trial will include adults from 17 medical facilities of Kaiser Permanente Northern California who make Paxlovid e-visits on weekdays from October 9 to December 11, 2023.

**Intervention.** In the intervention group, a regional team of pharmacists will manage Paxlovid evisits following a standard protocol; in the comparison group, adult and family medicine physicians (AFMs) will manage these visits according to medical center-based protocols.

**Main Outcomes and Measures.** The primary outcome is whether a patient with one or more common drug-drug interactions received counseling for any drug-drug interaction. Secondary outcomes are the hours from the e-visit request to the prescription among patients who receive one and the clinician time and cost per visit managed.

**Potential Results.** We will test the hypotheses that Pharmacist Care compared with AFM Pool Care will have higher quality of care and lower costs based on the receipt of counseling for common drug-drug interactions, faster time to prescriptions, and lower clinician time and cost per visit managed.

**Potential Conclusions and Relevance.** If pharmacist management has better or similar outcomes compared with AFM pool management, this will provide support to continue this practice for Paxlovid e-visits and to evaluate possible expansion of pharmacist management for similar clinical situations.

## 1. Specific Aims and Hypotheses

Enhancing message management and virtual urgent care options for patients are among TPMG and KFH's top priorities. As team-based inbox management is further developed, evaluating its clinical effectiveness and outcomes in terms of patient care experience and costs will provide valuable information for operational planning. In addition, sharing what we learn with other health care systems through talks and publications will help highlight TPMG's reputation as a group that innovates to support clinicians while increasing patient access through virtual care.

This study will compare the clinical outcomes and costs of two alternative modes of management of patient requests for Paxlovid sent via e-visits: management by a regional team of pharmacists, vs. management by medical center-based pools of adult and family medicine physicians (AFMs) doing desktop medicine. We will conduct a cluster randomized trial in 17 facilities in Kaiser Permanente Northern California to compare Pharmacist Care with AFM Pool Care for patients making Paxlovid e-visits with regard to:

Aim 1. Quality of care

Example hypothesis: Patients with common potential DDIs will be more likely to receive relevant counseling in the Pharmacist Care group than the AFM Pool Care group.

Aim 2. Clinician time and costs

Example hypothesis: Pharmacist Care will have lower costs of clinician time per Paxlovid e-visit managed than AFM Pool Care.

Aim 3. Exploratory outcomes

Example hypothesis: Patients in the Pharmacist Care will report comparable satisfaction with the process compared with the AFM Pool Care group.

## 2. Background and Significance

Physicians experience substantial stress associated with managing their electronic health record (EHR) inboxes. Much of physicians' time in the EHR inbox involves answering messages from patients. The volume of messages is a key driver of stress and attention switching.

Assisting physicians with message management is a top priority for The Permanente Medical Group (TPMG). A variety of approaches are possible. Team-based approaches that involve pharmacists and other clinical staff have been recommended, and anecdotal report suggests they have been successful in some settings. However, scant systematic evidence exists on whether such approaches are effective in terms of timeliness or quality of care, or in actually saving physicians' time.

This study will address this important gap in evidence via a cluster randomized trial comparing pharmacist management of patient e-visit requests for nirmatrelvir-ritonavir (Paxlovid) with management by pools of adult and family medicine (AFM) physicians. The latter was the default approach by most Kaiser Permanente Northern California (KPNC) medical centers before 2023. The findings will have broad implications for regional care delivery planning, as TPMG and KFH consider whether and how to have pharmacists and other clinical team members participate in message management. This study will inform operational decisions and practice for both Kaiser Permanente and other health care systems in the U.S. and beyond.

## 3. Innovation

Pharmacist management of secure messages from patients is innovative in not having been adopted or evaluated at large scale. Preliminary anecdotal and unpublished information from within TPMG suggests that pharmacists' scope of practice is well-suited to message management for many specific conditions based on treatment algorithms. At our KP San Francisco medical center, pharmacists have been able to take charge of messages for a range of issues, including refill authorization requests and requests to manage chronic conditions (hypertension, osteoporosis, attention deficit disorder, gout) and time-limited conditions (sexually transmitted infections, latent tuberculosis, opioid tapering, and assessment of Paxlovid eligibility).

E-visit management is another innovative aspect of this study. Kaiser Permanente Northern California (KPNC) is ahead of most other systems nationally in its implementation of e-visits.

Enhancing the accessibility of urgent care through digital and other means is a key priority for TPMG as well as KP generally.

# 4. Approach

## 4.1. Design, setting, and participants.

This cluster randomized clinical trial will assign patient requests for Paxlovid made via e-visits to either Pharmacist Care or AFM Pool Care, which consists of management by medical centerbased pools of AFMs in adult and family medicine (AFM). The unit of randomization is the KPNC facility. KPNC is an integrated health care system with 4.6 million members served by more than 9,500 physicians and 87,000 employees in 15 service areas. It has a mature EHR (EPIC/HealthConnect, adopted circa 2008) and encourages members to use a wide array of options for outpatient care, including secure messages to physicians via the EHR portal, e-visits, video, telephone, and in-person office visits.

The target population is adults 18 years and older in facilities within participating KPNC service areas who submit requests for Paxlovid on weekdays during the study period using the e-visit protocol accessible via the electronic portal kp.org. Messages that are handled from 8:00 am to 4:30 pm, Monday through Friday will be included. The study period will run from October 9 to December 11, 2023. Pharmacist Care will not be available for Paxlovid e-visits that need to be reviewed on weekends or holidays. These are managed by virtualist physicians in the regional call center and will be excluded from this study.

Of KPNC's 15 service areas, 4 have not implemented pharmacist management in any facility. These service areas and their facilities are eligible for this study; others must be excluded. The eligible service areas are SCL, SJO, SRF, and SSC. These service areas contain 17 facilities; each facility will be treated as a cluster in the random assignment process.

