#### 4.4. Main outcomes and measures

#### 4.4.1. Outcomes

The primary outcome will be measured only among patients who have common potential drugdrug interactions (DDIs) based on a pre-specified list of medications. The outcome will be whether the patient received counseling for any valid potential DDI. For patients with more than one DDI, the outcome will counted as present if they received counseling for any of their potential DDIs.

Secondary outcomes will be:

- a. % of all patients who were prescribed Paxlovid (based on orders)
- b. Hours from the e-visit request to the prescription order being placed, among patients who were prescribed Paxlovid
- c. Clinician minutes per message handled. This will be analyzed using EPIC access log data. We will link each e-visit for Paxlovid with the relevant secure messages and/or

telephone encounters, including follow-ups that occurred before the initial request was resolved. Clinicians include pharmacists and physicians.

- d. Estimated personnel cost per Paxlovid message handled. The estimated cost per message handled will be calculated by multiplying the number of minutes spent per message by the standard wage rate for a pharmacist or AFM in Northern California.
- e. Patient satisfaction with care

Exploratory outcomes will be:

- a. Number of Paxlovid e-visits handled by the regional pharmacy team, per week
- b. % of messages fully handled by the initial clinician (pharmacist or AFM) (based on review of visits)
- c. % of cases handled by pharmacists that required a physician consultation (based on review of visits)
- d. Pharmacist satisfaction with the process of care [Note: Deleted "AFM satisfaction" as a measure because there was not a logical group of AFMs to survey, nor logical questions to ask them.]
- e. % of all patients who obtained Paxlovid (based on fills)
- f. Days from request to receipt of medication among patients prescribed Paxlovid
- g. % of patients with common potential DDIs who were prescribed Paxlovid
- h. If feasible based on ICD-9 codes: Incidence of drug reactions due to Paxlovid DDIs within 10 days after a Paxlovid prescription

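### Eligibility turns on when a message is handled, an undefined event that depends on response speed, so exclusions could differ by arm and bias hours to prescription

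*Combined protocol and SAP*

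**What the plan says.** Section 4.1 sets three conditions that need not coincide. The target population is adults "who submit requests for Paxlovid on weekdays during the study period", with no hours given for submission. The next sentence adds that "Messages that are handled from 8:00 am to 4:30 pm, Monday through Friday will be included". The section then says that "Pharmacist Care will not be available for Paxlovid e-visits that need to be reviewed on weekends or holidays", and of those e-visits that "These are managed by virtualist physicians in the regional call center and will be excluded from this study".

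Handling is never tied to an EHR event. Section 4.4.1 implies that one message can have several. Clinician minutes are counted over linked encounters, "including follow-ups that occurred before the initial request was resolved", and an exploratory outcome is the percentage "of messages fully handled by the initial clinician (pharmacist or AFM"). Section 4.6 uses first access, but only to group patients.

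Secondary outcome b is "Hours from the e-visit request to the prescription order being placed, among patients who were prescribed Paxlovid". The Abstract hypothesises that Pharmacist Care will have "faster time to prescriptions, and lower clinician time and cost per visit managed".

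**The concern.** Handling time is submission time plus response delay, whether handling means first access, the order or resolution. Outcome b is the delay from request to order. The rule therefore selects e-visits on the outcome or on a component of it, after assignment, in a trial whose hypothesis is that this delay differs between arms.

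The documents do not say what either team does with a message still open at 4:30 pm. Nor do they say what happens on Fridays or before holidays, when an open message might count as needing weekend or holiday review and so be excluded. The period from October 9 to December 11, 2023 contains 46 weekdays, 9 of them Fridays. Identical practice cannot be presumed: section 4.2 describes one regional pharmacist team on one side, and physician pools by service area, with any local protocols, on the other.

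At stake is the comparison of hours to prescription, chiefly in the assignment-based analysis of section 4.6. That analysis cannot restore e-visits removed before it starts, and section 4.6 plans no analysis of these exclusions. The first-access analysis is already a non-randomised grouping.

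**Working it through.** **The plan's own count.** Section 4.8 gives 1,089 e-visits per week. 1,089 × 5/7 = 778; 778 × 0.25 = 194.5, taken as 195; 195 × 8 weeks = 1,560; 1,560/17 = 91.8, or 92 per cluster. The figure reproduces. The chain removes weekends only and deducts nothing for handling hours.

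**What has to be assumed.** The documents give no response times, no staffing after 4:30 pm and no distribution of submission times. For illustration: submissions even over 8:00–16:30, Monday to Friday; exponential delay counted in team hours, mean 1 h (fast arm) and 3 h (slow arm); neither team works weekends; handled means order placed. Friday leftovers go either to Monday 8:00 or to virtualists (Saturday 8:00 plus an exponential delay of mean 2 h, then excluded). Prescribing is taken as independent of delay. Each workflow was simulated with 2 million e-visits per arm.

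**Hand check of one case.** In workflow B an e-visit is excluded when its delay exceeds the working time left in the week, which is uniform on 0 to 5 × 8.5 = 42.5 h. The share is (m/42.5) × (1 − exp(−42.5/m)) for mean delay m. With m = 1 this is 2.4%; with m = 3 it is 7.1%.

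**Slow-minus-fast mean hours:**

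| Workflow | All e-visits | Handled in window | Change | Excluded, fast / slow |
|---|---|---|---|---|
| A: both stop at 16:30, Friday carried to Monday | 7.89 | 7.89 | 0% | 0% / 0% |
| B: as A, Friday leftovers to virtualists | 5.49 | 4.88 | −11% | 2.4% / 7.1% |
| C: both work to 20:00, Friday leftovers to virtualists | 3.19 | 2.85 | −11% | 11.5% / 25.3% |
| D: both work to 20:00, Friday to Monday | 4.20 | 4.53 | +8% | 11.4% / 23.3% |
| E: fast arm to 20:00, slow arm to 16:30, Friday leftovers to virtualists | 7.29 | 6.41 | −12% | 11.5% / 7.1% |
| F: fast arm to 16:30, slow arm to 20:00, Friday to Monday | 1.31 | 1.54 | +18% | 0% / 23.3% |

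**Sensitivity.**
- In B, with submissions even over 24 h on weekdays, 1 against 3 h gives 3.66 → 3.48 (−5%); 1 against 2 h gives 1.70 → 1.66 (−2%); 1 against 1.25 h gives 0.40 → 0.40 (nil).
- With handled read as first access, the delay splits into waiting and processing (fast arm 0.5 h each). B gives 5.55 → 4.97 (−10%), 5.59 → 5.39 (−4%) or 5.54 → 5.61 (+1%) as the slow arm's split moves from 2.5 + 0.5 h through 1.5 + 1.5 h to 0.5 + 2.5 h. The largest change in C is 2.88 → 2.24 (−22%). A is unchanged.

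The sign of the change depends on workflow, and so does which arm loses more e-visits: in E it is the faster one. In none of A to F does the between-arm difference itself change sign.

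**The case against.** The strongest reply is that section 4.1 merely describes service hours. Beside weekday submission and the remark on weekend review, the sentence can be read as saying when the teams operate, with anything left at 4:30 pm taken up at the next weekday session. Section 4.8 fits this, since it counts by weekday and deducts nothing for hours. Section 4.5 draws all e-visits in the period from the EHR. Under that reading the effect is exactly nil (workflow A). Workflows C to F also assume evening work, which the documents never mention, and the −11% in B halves if requests arrive round the clock.

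Much of this stands, and it limits what can be claimed about size. It does not remove the point. The sentence is worded as an inclusion rule, section 4.5 describes a data source without repealing it, and Friday and pre-holiday leftovers stay open even with no evening work.

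It also stands that a compulsory submission window with a Friday cut-off would be a poor remedy. With a Friday-noon cut-off, workflow A moves from 7.89 to 6.29 h (−20%), although the rule itself did no harm there. If submissions are even over 24 h and the window is 8:00–16:30 with that cut-off, 1,560 × (4 × 8.5 + 4)/120 = 494 remain. With detectable effect 2.802 × 2 × √(DE/n) and DE = 1 + (n/17 − 1) × 0.01, this goes from 0.196 SD at 1,560 to 0.285 SD at 494, against 0.20 SD stated for Aim 2 in section 4.8.

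**Conclusion.** The concern holds as a conditional one. Inclusion depends on an undefined post-assignment event linked to the delay that outcome b measures. If either team handles messages after 4:30 pm, or open Friday or pre-holiday messages pass to virtualists, exclusions can differ by arm and bias hours to prescription. If both teams carry every open message to the next weekday session, the effect is nil.

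A reader might infer more, and the documents do not support it:
- That the comparison is known to be biased, or biased towards no difference. Without response times or staffing hours, neither size nor direction can be determined; the percentages above are illustrations.
- That the slower arm must lose more e-visits. Workflow E shows otherwise.
- That sections 4.5 and 4.8 contradict section 4.1. A data source and a projection without an hours deduction are both compatible with it.
- That the DDI counseling result is affected. Nothing here shows an effect on the primary outcome.

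This is a cheap improvement to one secondary outcome.

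**What to change.** Before outcomes are analysed:

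1. Define eligibility by the submission timestamp: a non-holiday weekday in the study period, the same rule in both arms. This is what the target-population sentence in section 4.1 already says.
2. For outcome b in the assignment-based analysis, keep every such e-visit whenever and by whomever it was handled. This narrows the exclusion of virtualist-managed e-visits in section 4.1, so the text should say so.
3. Report by arm how many were handled outside 8:00 am to 4:30 pm or by virtualists.
4. In the first-access analysis, do not count virtualist-first e-visits as AFM physician care.
5. Show the handled-in-window set as a sensitivity analysis, with handling tied to one named EHR timestamp.

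Do not impose an 8:00–16:30 submission window or a compulsory Friday or pre-holiday cut-off; these change the population and may cost substantial sample. A Friday cut-off can be at most an optional sensitivity analysis.

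The cost is a query change. Section 4.5 already plans to identify all e-visits from EHR data and to use access logs for the following 5 days. The downside is some dilution of the assignment-based contrast by virtualist-handled e-visits, by an amount the documents do not allow to be estimated. Outcome b also remains conditional on a prescription, a separate selection that this change does not remove.

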# 4.2. Intervention.

All procedures will be conducted as part of standard of care. In the Pharmacist Care group, each e-visit message requesting Paxlovid will be assigned to a pharmacist on the regional team. Pharmacists will review requests using a standard protocol. They will call patients via telephone to elicit additional information where needed, file Paxlovid prescriptions when appropriate, and arrange home delivery when requested.

The protocol for pharmacists has a list of common potential drug-drug interactions and provides guidance for how these should be handled. Drug-drug interactions are documented by pharmacists using a smartphrase in Epic, the electronic health record (EHR). Some DDIs may lead to changes in medications while a patient is taking Paxlovid.

In the AFM Pool Care group, each e-visit message requesting Paxlovid will be assigned to a pool of AFM physicians based at the medical centers in a given service area. Physicians will review requests using the existing standard regional protocol (as well as any existing medical center-level protocols). The regional Paxlovid E-visit User Guide illustrates how to use SmartSets to document the plan and respond to patients with the outcome (eligible, not eligible, or further discussion needed). Following this protocol, physicians call patients via telephone to elicit additional information where needed, file Paxlovid prescriptions when appropriate, and arrange home delivery when requested.

4.3. Randomization. In each of the participating service areas, facilities have been assigned at random to either the Pharmacist Care or AFM Pool Care group. We used covariate-constrained randomization, a method to prevent imbalances on important variables that may be associated with the outcomes. We conducted preliminary analyses to characterize facilities with regard to population size, socioeconomic status (using the Neighborhood Deprivation Index), race, ethnicity, and COVID-19 incidence in the service area since the start of the pandemic. We have chosen these variables for use in the restricted randomization given the expected association with study outcomes, along with the expected level of between facility variability which would increase the likelihood of between-arm imbalance. We also stratify randomization on service area for within-area balance on number of facilities assigned to the Pharmacist Care and AFM Care groups.

Using these variables, we enumerated all possible outcomes of randomization and eliminated all allocations of the facilities to the two groups that do not meet specified between-group balance criteria. Standard diagnostics were applied in selecting the covariate balance criteria, ensuring no threats to the validity of the study design, including extreme reductions in total possible allocations for the trial, and instances of cluster pairs never/rarely or always/often randomized to the same arm. An allocation of facilities to the two arms for implementation was randomly selected from the set of allocations that meet the final covariate balance criteria.

The balance criteria were: maximum 5% between arm difference in total membership, 30% difference in total Black, 20% for each of White, Asian and Hispanic race/ethnic groups, 25% difference in mean NDI, and 15% difference in mean COVID-19 incidence. We are applying no between arm balance criteria within strata/service area.

The selected randomization scheme leads to good balance between the intervention and comparison groups, with 4.8% difference in total membership (~565K vs ~513K), 11.7% for Black (23K vs 29K), 2.2% for White (183K vs 175K), 8.7% Asian (150K vs 126K), 7.8% Hispanic (127K vs 109K), 12.2% difference in mean NDI (-.49 vs - .44), and 2.7% difference in mean COVID-19 incidence (.23 vs .22).

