#### 4.5. Data collection.

The primary outcome will be measured only among patients who have common potential drugdrug interactions (DDIs) based on a pre-specified list of medications. The outcome will be whether or not they received relevant counseling for any of their DDIs. Eligible patients in both groups will be selected using computerized pharmacy codes generated based on the protocol used by the regional pharmacy team. The computerized pharmacy codes will be used to identify patients with any of these potential DDIs in a consistent way in the Pharmacist Care and AFM Pool Care groups.

Research assistants blinded to group assignment will review text extracts from the EHR using a structured protocol to identify whether there is documentation that the patient received counseling regarding a DDI. With each study group, a random sample of eligible patients will be identified; the sample will be stratified by facility to yield a representative sample. Masking of group assignment will be conducted by one research assistant prior to review by a different

research assistant. A patient with any potential DDI will be counted as having received relevant counseling if any counseling (for any potential DDI) was documented in the text extra prior to or coincident with a Paxlovid prescription, or in the absence of a Paxlovid prescription, occurring within 2 days after the e-visit.

For the secondary outcomes, we will use data available from KPNC computerized sources, including HealthConnect (HC, aka EPIC) EHR data (from Clarity) and EPIC access logs. EHR data will be used to identify all e-visits for Paxlovid during the study period. For each patient who made an e-visit, the EPIC access log data for the subsequent 5-day period will be analyzed to identify how many minutes of pharmacist or physician time were associated with that request.

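### The primary outcome is defined as DDI counselling received but scored as counselling documented, and the plan does not examine whether the two groups document equally completely.

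*Combined protocol and SAP*

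**What the plan says.** Section 4.4.1 (Outcomes) states the outcome as something that happened to the patient: "The outcome will be whether the patient received counseling for any valid potential DDI".

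Section 4.5 (Data collection) states how it is scored. Blinded research assistants use a "structured protocol to identify whether there is documentation that the patient received counseling regarding a DDI". A patient with any potential DDI is positive "if any counseling (for any potential DDI) was documented" in the extract within the stated time window.

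Section 4.2 (Intervention) describes how each group records its work. For pharmacists there is a protocol listing common DDIs with guidance, and: "Drug-drug interactions are documented by pharmacists using a smartphrase in Epic, the electronic health record (EHR". For AFM physicians: "The regional Paxlovid E-visit User Guide illustrates how to use SmartSets to document the plan and respond to patients with the outcome". The outcomes named there concern eligibility or the need for further discussion. No DDI-specific documentation aid is mentioned for physicians, and the contents of the SmartSets, the User Guide and any medical-center protocols are not reproduced.

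Section 4.5 also provides common pharmacy codes to select patients in both groups, and masking of group by one research assistant before review by another.

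**The concern.** Received and documented are treated as the same thing. They are interchangeable for a between-group comparison only if the share of delivered counselling that reaches the chart is similar in both groups. The plan describes a DDI charting aid for one group and none for the other, so that similarity cannot be taken for granted.

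The primary analysis in section 4.6 groups patients by the type of clinician who first accessed the e-visit, so the comparison lines up closely with who would use the smartphrase. The assignment-based secondary analysis uses the same scored outcome and does not remove the problem.

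The abstract reads this outcome as quality of care, and the projected-impact section says the findings will inform how pharmacist effort is deployed. A difference in charting could therefore be read as a difference in care.

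**Working it through.** **Inputs from section 4.8.** Pharmacist counselling rate 0.70; clinically meaningful RR 0.8, so a physician rate of 0.70 × 0.8 = 0.56; 250 patients per group; two-sided alpha 0.05; ICC 0.01. Section 4.1 gives 17 facilities.

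**Step 1: the plan's own figure.**
- Reviewed patients per facility: 500/17 = 29.4.
- Design effect: 1 + (29.4 − 1) × 0.01 = 1.284.
- Effective n per group: 250/1.284 = 194.7.
- For 0.70 vs 0.56, pooled p = 0.63. SE under the null = √(2 × 0.63 × 0.37/194.7) = 0.0489. SE under the alternative = √((0.70 × 0.30 + 0.56 × 0.44)/194.7) = 0.0484.
- Power = Φ((0.14 − 1.96 × 0.0489)/0.0484) = Φ(0.91) = 0.82.

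The planned 80% is reproduced. Going the other way, the two-proportion formula needs 186 per group, or 200 with continuity correction. Multiplied by 1.284 these give 239 and 257, either side of 250. The sample size is not in dispute.

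**Step 2: unequal documentation with no true difference.** Scored rate = true counselling rate × share of delivered counselling that is charted. Assumptions, none of them in the documents: true rate 0.70 in both groups, pharmacist charting complete, no false positives. The formula of step 1 then gives:

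| Physician documentation | Scored rates | Scored RR | Chance of a significant result favouring pharmacists |
|---|---|---|---|
| 95% | 70% vs 66.5% | 0.95 | 11% |
| 90% | 70% vs 63% | 0.90 | 31% |
| 85% | 70% vs 59.5% | 0.85 | 58% |
| 80% | 70% vs 56% | 0.80 | 82% |

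With no difference in either counselling or charting, the figure in the last column would be about 2.5%. Counting both tails changes the 95% row only slightly: 0.111 + 0.003 = 0.115, hence 11-12%.

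**Step 3: other assumed values.** With pharmacist documentation at 95%, physician documentation of 85% gives 66.5% vs 59.5% (RR 0.89, chance 30%), and 76% gives 66.5% vs 53.2% (RR 0.80, chance 77%). With documentation of 100% vs 80% and true rates from 60% to 90%, the chance runs from 66% to 99.6%.

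**Step 4: what a tipping-point calculation would show.** Let r be physician completeness relative to pharmacist completeness. The corrected RR is the scored RR divided by r. Suppose the trial scored exactly 70% vs 56%. Then SE(log RR) = √((0.30/0.70 + 0.44/0.56)/194.7) = 0.079, and the 95% interval for the RR is 0.8 × exp(±1.96 × 0.079) = 0.69 to 0.93. The interval reaches 1 once r falls to about 0.93, and the point estimate reaches 1 at r = 0.80.

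All steps use a normal approximation with equal groups. The planned mixed model, and grouping by first-accessing clinician, would shift the numbers somewhat.

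**The case against.** The strongest reply is that unequal tooling is inferred from silence. Physicians do have a structured tool and follow regional and possibly local protocols whose contents are not shown. DDI text may well be in them. Section 4.2 also has physicians reply to the patient, and advice sent in writing documents itself. Telephone calls are described in the same terms for both groups, for the purpose of gathering information, so uncharted telephone advice peculiar to physicians is conjecture. Section 4.6 allows referral in both directions, so smartphrase text need not stay in one group. All of this stands. It means a charting gap is possible, not shown.

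The 80% row is also built to land on the plan's RR, since 0.70 × 0.80 = 0.56. That stands too: the table shows sensitivity, not likely bias.

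Blinded review, the structured form and common patient selection do not answer the point. They protect against reviewer and selection bias, not against counselling that never reached the chart. The survey items in section 4.5 cover satisfaction, timeliness and confidence, with none on DDI advice received, and no other check of completeness is described.

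Two stronger readings are tempting. A reader might infer that smartphrase text will be scored as counselling where none took place. The documents say that the smartphrase records interactions, not that it records counselling, and the review form's handling of template text is not given. A reader might also infer that the scoring rule should be tightened to exclude template text. That is a trade-off: it cannot recover uncharted physician advice, may penalise brief free-text notes, and could reveal the group to reviewers.

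**Conclusion.** The point holds in this limited form. The outcome as defined and the outcome as scored differ; a DDI documentation aid is described for pharmacists only; and nothing in the plan measures or bounds unequal charting. If physicians document less completely, the bias favours pharmacists.

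Its size is unknown. Under the assumptions of step 2, the chance of a significant result with no true difference runs from about 11-12% at 95% physician documentation to 82% at 80%.

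The documents do not support the claim that physicians lack any DDI documentation tool. Nor do they support the claim that a positive result could never be distinguished from better charting: that depends on how large the scored effect is relative to a plausible documentation gap, which is what a tipping-point analysis would show.

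**What to change.** - **Sections 4.4.1 and 4.6:** name the primary outcome 'documented DDI counselling' and limit the conclusion to that. The abstract's wording should follow.
- **Section 4.6:** add a tipping-point sensitivity analysis, specified before the outcome is compared between groups. Over a range of physician-group completeness relative to the pharmacist group, report the corrected effect and its interval. State the level at which the interval first includes no difference and the level at which the estimate itself reaches it.
- **Section 4.5:** keep the existing blinded scoring rule as primary.

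The cost is one extra analysis on data the plan already collects, with no new chart review, and a more modest conclusion: a positive trial would show more documented counselling, with a statement of how much under-documentation by physicians would be needed to explain it.
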